### **7.3.1.5 Treatment Compliance**

Compliance with study medication—based on the drug accountability data—will be calculated as the number of days subjects take study medication divided by the duration of exposure in days, expressed as a percentage.

Study medication compliance will be calculated as follows:

$$\frac{\text{Cumulative Dosing days}}{(\text{date of end of treatment visit} - \text{date of first dose in A02})} \times 100\%$$

The subjects should take one dose daily per protocol.

## **7.3.2 Safety Assessments**

### **7.3.2.1 Adverse events (AEs)**

An AE is any untoward medical occurrence in a subject or clinical investigation subject administered a pharmaceutical product that does not necessarily have a causal relationship with this treatment.

AEs will be coded using Medical Dictionary for Regulatory Activities (MedDRA) central coding dictionary, Version 20.1.

Treatment-emergent AEs (TEAEs) are defined as AEs that started or worsened in severity on or after the first dose of study medication. The treatment relationship with the AE is in 2 categories (reasonable possibility, no reasonable possibility). The detail is included in protocol.

### **7.3.2.2 Adverse Reactions**

Adverse reactions are defined as adverse events that are determined to have a “reasonably possible” causal relationship to the study drug.

### 7.3.2.3 Duration of the AE and Time to the AE

Duration of the AE and time to the AE occurrence from start of study A02 medication will be calculated and presented in days, where AE duration = AE stop date – AE start date + 1 and the time to the AE occurrence = AE start date – first study A02 dose date + 1.

### 7.3.2.4 The Estimated Glomerular Filtration Rate (eGFR)

$eGFR = 141 \times \min(S_{Cr}/\kappa, 1)^\alpha \times \max(S_{Cr}/\kappa, 1)^{-1.209} \times 0.993^{Age} \times 1.018$  [if female]  $\times 1.159$  [if Black]

$S_{Cr}$  (standardized serum creatinine) = mg/dL

$\kappa$  = 0.7 (females) or 0.9 (males)

$\alpha$  = -0.329 (females) or -0.411 (males)

min = indicates the minimum of  $S_{Cr}/\kappa$  or 1

max = indicates the maximum of  $S_{Cr}/\kappa$  or 1

Age = years

It will be rounded off the second decimal place and reported the value to the first decimal place.

### 7.3.2.5 Lab values Below/Above the Limit of Quantitation Deriving

The lab values below the limit of quantification (BLQ) are collected in the form like “< 2” in the clinical data base. In this case the numeric value of the lab is missing value. The cut-off value ‘2’ will be used to impute the missing value for this case. Similarly, for the lab values above the limit of quantification, the cut-off value will be used for the numeric value of the lab.

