## **6. GENERAL CONSIDERATIONS**

### **6.1 Descriptive Statistics**

Continuous data will be summarized descriptively using the number of observations, mean, standard deviation (SD), median, minimum and maximum. Categorical data will be summarized using frequency counts and percentages. The denominator for the percentages will be the total number of subjects in the treatment group and analysis population being presented, unless otherwise specified.

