**Table 4 Imputation of lab values below/above the limit of quantification**

Lab Test	Characteristic value	Derived Numeric value
Bilirubin	<2	2
Direct Bilirubin	<2	2
Estradiol	<61	61
Luteinizing Hormone	<0.1	0.1
Specific Gravity	>1.045	1.045

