### 8.2.2 Laboratory Tests

For all continuous laboratory parameters, the lab values and change from baseline to post baseline visits are summarized by treatment group of A01 and overall and visit.

For all discrete laboratory parameters, the lab values are summarized with count and percentage by treatment group of A01 and overall and visit.

The lab tables will be generated for each Lab categories (Hematology, Biochemistry, Coagulation, Urinalysis and Hormones).

(Table 14.3.2.1, Table 14.3.2.2, Table 14.3.2.3, Table 14.3.2.4, Table 14.3.2.5)

All laboratory data will be listed with clinically relevant values flagged (L=Lower than lower limit of normal range or H=Higher than upper limit of normal range).

In addition, following clinical relevant ranges (and flags) will also be considered for summary table. The count and percent of subjects meeting the criteria will be presented. (Table 14.3.2.6)

- ALT  $\geq 3 \times$  Upper Limit of Normal Range (ULN), 5 $\times$  ULN, 8 $\times$  ULN, 10 $\times$  ULN
- AST and/or ALT  $\geq 3 \times$  ULN, 5 $\times$  ULN, 8 $\times$  ULN, 10 $\times$  ULN
- AST and/or ALT  $\geq 3 \times$  ULN with Total bilirubin  $\geq 2 \times$  ULN
- Total bilirubin  $\geq 2 \times$  ULN
- Creatinine  $\geq 2 \times$  ULN

The all clinical lab tests will be listed.

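### Estradiol results below 61 are analysed as 61, so change from baseline across the limit is understated, and no planned summary shows how many values are affected

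*SAP*

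**What the plan says.** SAP 7.3.2.5 explains that a result below quantification is stored as text with a less-than sign and has no numeric value. The cut-off "will be used to impute the missing value for this case". Table 4 applies this to five tests. Two are reproductive hormones: "Estradiol <61 61" and "Luteinizing Hormone <0.1 0.1". The table gives no units.

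SAP 8.2.2 handles tests with a continuous scale as follows: "the lab values and change from baseline to post baseline visits are summarized by treatment group of A01 and overall and visit". The laboratory categories are "Hematology, Biochemistry, Coagulation, Urinalysis and Hormones". By the order in which the tables are listed, hormones are Table 14.3.2.5. SAP 6.1 sets the statistics: "number of observations, mean, standard deviation (SD), median, minimum and maximum".

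SAP 2.2.1 places reproductive hormones among the safety endpoints that serve the primary objective. SAP 7.2 defines baseline as the last assessment before the first A02 dose.

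The text supplied plans no count of unquantifiable estradiol results, no table of movement across the limit, no alternative substitution and no censored-data method. The threshold table, 14.3.2.6, covers only liver tests and creatinine.

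**The concern.** A substituted 61 is a bound, not a measurement, but in the hormone table it counts as a measurement. The reader cannot tell a mean change near zero that reflects stable estradiol from one that arises because most results sit at the limit at both visits.

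Estradiol belongs to the safety set on which the primary objective rests. The study is descriptive, so the hormone table is the group-level evidence on this parameter. If many results are unquantifiable, which the documents neither state nor exclude, a real shift could appear much smaller than it was, with nothing in the table to warn the reader.

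**Working it through.** The SAP gives no figure to reproduce. The Table 4 entries do follow the rule in 7.3.2.5.

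**Inputs from the documents.** Limit L = 61 for estradiol and 0.1 for LH (SAP Table 4). The substituted value is L itself (SAP 7.3.2.5). Change is follow-up minus baseline (SAP 8.2.2).

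**Step 1: one subject.** The rule replaces a true value x by f(x) = max(x, 61).

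- Below the limit at both visits: 61 − 61 = 0, whatever happened underneath.
- Rise from x < 61 to y ≥ 61: recorded y − 61, true y − x, understated by 61 − x.
- Fall from x ≥ 61 to y < 61: recorded 61 − x, true y − x, so the size is understated by 61 − y.

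For every pair, |f(y) − f(x)| ≤ |y − x|. In 400,000 random pairs the recorded change never exceeded the true change in size. Two rises from below the limit:

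| Follow-up | Recorded | True change lies between |
|---|---|---|
| 70 | 70 − 61 = +9 | just above +9 and +70 |
| 100 | 100 − 61 = +39 | just above +39 and +100 |

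The rule thus records the smallest rise compatible with the data.

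**Step 2: the group mean, one-directional shift.** Let S_X(t) and S_Y(t) be the proportions above t at baseline and follow-up. True mean change is the integral of S_Y − S_X over all t > 0. The planned mean change is the same integral over t > 61 only. If the whole distribution moves one way, the planned change cannot be larger in size than the true one.

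Example with assumed values: 10% of subjects go from 30 to 90 and the rest stay at 30.

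- True mean change: 0.10 × (90 − 30) = +6.0.
- Planned: 0.10 × (90 − 61) = +2.9.
- With L/2 = 30.5 substituted: 0.10 × (90 − 30.5) = +5.95.

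**Step 3: the group mean, mixed changes.** Two subjects: 70 to 100, and 50 to 20. True mean change: (30 − 30)/2 = 0. Planned: (30 + 0)/2 = +15. Here the planned mean moves away from zero.

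**Step 4: how size depends on the share below the limit.** Everything in this step is assumed: lognormal values, log-SD 0.5 or 0.8, correlation 0.6 between visits, and a true 1.5-fold rise. The table gives the percentage of the true mean change that is recovered.

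| Below limit at baseline | Planned rule | L/2 |
|---|---|---|
| 50% | 82–86% | 100–108% |
| 70% | 66–71% | 92–101% |
| 90% | 37–42% | 66–74% |
| 95% | 24–28% | 49–55% |

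The SD of change usually shrinks but not always. With 90% below the limit, log-SD 0.5 and no shift, it is 18.0 true and 9.3 planned. With 50% below, log-SD 0.5 and a 2-fold rise, it is 60.6 true and 62.2 planned.

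**Step 5: LH.** The same algebra with L = 0.1 caps the error for any subject at 0.1 reported unit.

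**The case against.** The strongest reply is that the rule is prespecified and open, and that other outputs limit the harm.

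- A minimum or median of 61 hints at substituted values, and the maximum is unaffected while any result is quantifiable.
- All laboratory data are listed with high and low flags (SAP 8.2.2), and clinically significant abnormalities become adverse events (Protocol 6.5.7 and 8.5.1).
- Endometrial thickness, biopsy and breast findings are summarised directly (SAP 8.2.6 and 8.2.7).
- For the estradiol level itself, the rule errs high rather than low.
- No hypothesis or decision rule is attached to the hormones.
- Table shells are not in the supplied text and some SAP contents entries are blacked out, so only the visible text can be called silent.

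All of this stands, and it keeps the point small. None of it corrects the mean change or shows, at group level, how many subjects moved across the limit.

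A reader might infer several stronger things that the documents do not support:

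- **Mean change is always pulled toward zero, or the SD always shrinks.** Steps 3 and 4 give counterexamples.
- **The upward bias in the baseline mean measures the bias in change.** With an assumed 25–75% below the limit and an assumed true mean of 30 among them, the baseline mean is too high by 0.25 × 31 = 7.8 to 0.75 × 31 = 23.3 units. The same substitution applies at follow-up, so this cancels in the change if the distribution is unchanged, and partly otherwise.
- **An estradiol rise is the plan's stated worry.** The visible text lists hormones as one of nine unranked safety domains and names no direction.

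**Conclusion.** The point holds for estradiol as a reporting weakness. For each subject, the recorded change is never larger than the true one. A rise out of the unquantifiable range is understated by 61 minus the true baseline, up to 61 reported units, and falls into that range are understated likewise. For the group mean, attenuation is certain only under a one-directional shift; with mixed changes the distortion can go either way.

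The practical size cannot be fixed from the documents, because they do not give the share below the limit. Under the assumed shares of 50% to 95%, it runs from modest to severe; with few unquantifiable results it would be trivial. That uncertainty is itself the reason to report the count. LH can be left alone. This is a cheap improvement, not an error that threatens a planned conclusion.

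**What to change.** In Table 14.3.2.5, for estradiol only:

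1. Add n (%) below the limit at each visit.
2. Add a baseline-to-EOT shift table with two categories, below limit and quantifiable.
3. Print the median and minimum as <61 when they fall at the substituted value.
4. Footnote that mean change uses substitution at the limit.
5. Add one sensitivity summary, using L/2 or a censored-data estimate.

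Items 1 and 2 matter most. L/2 is also arbitrary: it overstated the size of change in about 21% of random pairs (both values uniform on 0 to 200), and it too gives +15 in the two-subject example. It serves to show sensitivity, not to replace the rule. No reporting device recovers movement that stays wholly below the limit.

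The change and shift tables need a Week 12 value. Footnote 1 to Protocol Table 2 restricts the hormones to Visits 3 and 6, while Protocol 5.2.1.1 and 5.2.1.3 list them at Visit 1 and EOT. These passages should be reconciled so that the baseline is defined.

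Cost: one count row, one small shift table and one extra summary, all from data already held. SAP section 4 has the plan finalised before database lock, so the change belongs there.

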**Table 4 Imputation of lab values below/above the limit of quantification**

Lab Test	Characteristic value	Derived Numeric value
Bilirubin	<2	2
Direct Bilirubin	<2	2
Estradiol	<61	61
Luteinizing Hormone	<0.1	0.1
Specific Gravity	>1.045	1.045

### 7.3.3 Exploratory Assessments

The subjects' diary data will be used to derive the efficacy endpoints. Subjects can use paper diary as contingent back up when they have problem with their ediary device. The paper diary data will be used only for the days that subjects have paper diary without ediary data. This means the paper diary data is not used when ediary data is available.

### 7.3.3.1 Average daily frequency of moderate to severe VMS

The average daily frequency of moderate to severe VMS at a time point (Week 12, 13, 14, ..., 64) is the average of the frequency of moderate to severe VMS of available diary days in a 7-day window. It will be rounded off the second decimal place and reported the value to the first decimal place. The nominal day for each time point relative to the first dose day will be used. The analysis windows are defined in the table below. The other efficacy endpoints based on average daily VMS diary data will be derived using these windows accordingly.

**Table 5 Analysis visit windows of diary days used for average daily frequency of moderate to severe VMS**

	Nominal day	Window
Week 12 (Baseline)	85	Day 79 to 85
Week k	$K^*7 + 1$	Day $K^*7 - 5$ to $K^*7 + 1$

where  $k = 13, 14, \dots, 64$ .

VMS data on the day of Week 64 visit is not used for the calculation of average daily VMS frequency.

If the count of available VMS data in a specific week is less than four (4), the latest diaries in the previous window can be carried as needed to make 4 diaries available in this window. Then the average daily VMS frequency in the week is calculated.

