4.1 Number of subjects

It is planned to enroll up to 364 subjects who have completed Study MT-8554-A01. The study will be finished when approximately 100 subjects complete a 52-week open-label treatment period and 30-day follow-up.

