5.2.1.3 Visit 6: EOT (Week 64 or early termination)

Subjects will attend the last visit of the treatment period and the following assessments will be performed (refer to Table 1 for further details):

- Physical examination (see Section 6.5.1)
- Breast examination
- Body weight
- Vital signs (including sitting blood pressure, pulse rate, and tympanic body temperature)
- 12-lead ECG
- Routine laboratory evaluations (hematology, biochemistry, coagulation, and urinalysis)
- Transvaginal ultrasound and Endometrial biopsy (for subjects with a uterus)
- Reproductive hormone assessments: E2, LH, and FSH
- PHQ-8 and GAD7
- MENQOL
- VMS diary collection
- Drug Accountability
- AE and concomitant medication recording.

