## **2.2.2 Exploratory Endpoints**

- Frequency of VMS, which is the average daily frequency of moderate to severe VMS, defined as the sum of the number of moderate to severe VMS during 1 week divided by number of days with data.
- Severity of VMS, which is the average daily severity score of mild to severe VMS. Baseline VMS severity score and VMS severity score for a specific week during the open label treatment period is defined as  $(1xFmi + 2xFmo + 3xFse)/(Fmi + Fmo + Fse)$ , where Fmi, Fmo, and Fse are the daily frequencies of mild, moderate, and severe VMS, respectively, during each applicable study week.
- MENQOL.

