### 7.3.3.2 Average daily severity score of mild to severe VMS

The daily VMS severity score is defined as  $(1xFmi + 2xFmo + 3xFse)/(Fmi + Fmo + Fse)$ , where Fmi, Fmo, and Fse are the daily frequencies of mild, moderate, and severe VMS, respectively. It will be rounded off the third decimal place and reported the value to the second decimal place.

The avarage daily VMS severity of mild to severe VMS at a time point (Week 12 (Baseline), 13, 14, ..., 64) is the average of the daily severity of available diary days in the corresponding 7-day window defined in Table 5.

A daily severity score of zero (0) is assigned if it is reported that no VMS occurred on that day. VMS data on the day of Week 64 visit is not used for the calculation of average daily VMS severity. If the count of available VMS data in a specific week is less than four (4), latest diaries in the previous window can be carried as needed to make 4 diaries available in this window. Then the average daily VMS severity in the week is calculated.

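### The SAP drops the visit-day diary entry only at Week 64, so a probably part-recorded day at an early-termination EOT visit counts as a full day and lowers that woman's last weekly VMS frequency

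*SAP*

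**What the plan says.** - SAP 7.3.3.1, under Table 5, on frequency: "VMS data on the day of Week 64 visit is not used for the calculation of average daily VMS frequency". SAP 7.3.3.2, on severity: "VMS data on the day of Week 64 visit is not used for the calculation of average daily VMS severity". Neither section gives a reason or mentions an early-termination visit.
- The weekly frequency "is the average of the frequency of moderate to severe VMS of available diary days in a 7-day window" (SAP 7.3.3.1). SAP 2.2.2 describes it as a sum "divided by number of days with data". No minimum recording time is set for a day to count.
- If a window has fewer than four diaries, "the latest diaries in the previous window can be carried as needed to make 4 diaries available in this window" (SAP, under Table 5).
- Protocol 5.2.1.3 defines Visit 6 (EOT) as taking place at Week 64 or at early termination, and lists "VMS diary collection" among its procedures. Footnote 4 to Table 1, in both documents, asks for the EOT visit from women who complete and from those who withdraw early.
- Protocol 9.1 says that women record VMS as an ongoing activity, not at one fixed time of day.

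**The concern.** A woman who hands in her diary at a clinic visit cannot record what happens later that day. If this is why the SAP drops the Week 64 visit day, the same reason applies at an early-termination visit, where the same procedure is carried out. The written rule protects only women who reach Week 64. For the others, events are counted up to the clinic visit while the denominator counts a whole day. The error runs in one direction: the last weekly frequency is too low, so the change from baseline looks too favourable. What is at stake is the last weekly value of each affected woman, in the listings and in that week's summary.

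**Working it through.** The documents state no figure for this bias, so there is none to reproduce.

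**Does the literal rule miss early EOT visits?** Table 5 assigns Day 7k-5 to Day 7k+1 to Week k. Week 64 is therefore Day 443 to 449 (64×7-5 and 64×7+1). An EOT visit on Day 300, for example, falls in Week 43 (43×7-5 = 296; 43×7+1 = 302). Table 3, which governs the other assessments, starts its Week 64 window at Day 408. A programmer following the text would have no instruction to drop the Day 300 entry.

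**Inputs**
- n, diary days averaged: 4 to 7 when the top-up to four is applied (SAP, under Table 5).
- f, share of the visit day's events recorded: not in the documents; assumed 0.25, 0.5, 0.75.
- Mean daily frequency: not in the documents; assumed 5 per day, and the same on every day averaged.
- Enrolment up to 364, and about 100 completers at study end (Protocol 4.1).

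**Bias in one woman's last weekly frequency.** With m events per day, the mean of n-1 full days and one part day is m(n-1+f)/n. The relative bias is -(1-f)/n.

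| f | n = 7 | n = 4 | Average over visit day |
|---|---|---|---|
| 0.75 | -3.6% | -6.25% | -5.4% |
| 0.50 | -7.1% | -12.5% | -10.8% |
| 0.25 | -10.7% | -18.75% | -16.2% |

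The last column takes the visit as equally likely on days d = 1 to 7 of the window, with n = max(d, 4). The mean of 1/n is (4×0.25 + 0.2 + 0.1667 + 0.1429)/7 = 0.2156, which is multiplied by (1-f). At 5 VMS per day and f = 0.5, the shortfall is 5×0.5/7 = 0.36 to 5×0.5/4 = 0.625 events per day.

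The top-up is worded as optional. Without it, n = d and the mean of 1/n is 2.5929/7 = 0.3704, so the average bias at f = 0.5 is 18.5%.

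**Bias in a weekly group mean.** Take the upper bound: 364 start, 264 leave evenly over 52 weeks (264/52 = 5.08 per week), and all of them are affected. At f = 0.5:
- first week: 5.08/364 × 10.8% = 0.15%;
- last week, with 364 - 51×5.08 = 105 women present: 5.08/105 × 10.8% = 0.52%;
- average over the 52 weeks: 0.26%.

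The average is 0.13% at f = 0.75 and 0.40% at f = 0.25.

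**Severity.** The daily score is a ratio, so a part day with the usual mix of mild, moderate and severe events leaves it unchanged. It falls systematically only if the day is reported as having no VMS and scores 0. At an assumed mean score of 2.0, the weekly value then drops by 2/n: 0.29 (n = 7) to 0.50 (n = 4).

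**The case against.** The strongest reply is that the Week 64 visit is Visit 6, which by definition includes early termination, so the rule may already be meant to cover both. That is possible. But the SAP names the alternative where it wants both: the ECG shift tables (8.2.4) refer to EOT or early discontinuation, and the biopsy shift table (8.2.7.2) to Week 64 or EOT. The wording is at best ambiguous and needs settling.

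It is also fair that part-recording is inferred. The SAP does not say so, and the diary example in the protocol's Appendix 3 is not in the text available. Ongoing recording and collection at the visit make it likely, not certain.

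Several stronger readings are tempting, and the documents do not support them:

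- **That every early leaver is affected.** Protocol 4.5.2 asks for EOT assessments only as far as possible, and women lost to follow-up may have none. Women who stop drug are encouraged to stay to the final visit (4.5.1), where the Week 64 rule covers them. A woman with no diary entry that day, or with all her VMS before the visit, is unaffected.
- **That most of the study is affected.** Protocol 4.1 says "The study will be finished when approximately 100 subjects complete a 52-week open-label treatment period and 30-day follow-up", and 364 - 100 = 264 (73%). But 364 is a cap, so 264 is a ceiling. Many of these women could still be on treatment when the sponsor closes the study, so their leaving would say nothing about lost benefit.
- **That severity is biased in general.** It is a ratio, as shown above.
- **That the paper-diary rule creates the same error.** SAP 7.3.3 adds: "This means the paper diary data is not used when ediary data is available". A device failing mid-day could lose paper entries, but the documents do not say how often or how much. Merging the two sources would need entry times that they do not show are recorded. Preferring one source for a whole day is also an ordinary way to avoid double counting.

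Finally, SAP 8.3 names no last-value summary, so the planned tables would barely change. That stands, and it limits the importance of the point.

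**Conclusion.** The point holds in a limited form. Followed literally, the SAP keeps the diary entry from an early-termination EOT visit as a full day while dropping the equivalent entry at Week 64. For a woman with such a visit and a part-recorded entry, the last weekly frequency is biased low by about 4% to 19%. This range rests on assumed f of 0.75 to 0.25, the top-up to four diaries and a constant daily rate. The effect on weekly group means is well under 1% even at the upper bound of early leavers. The endpoints are exploratory and summarised descriptively. This is a minor wording correction and raises no doubt about the study's conclusions.

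**What to change.** In SAP 7.3.3.1 and 7.3.3.2, define the excluded day as the day of the Visit 6 (EOT) visit, whether at Week 64 or early termination. In the same edit, state whether a week whose only diary day is the excluded one receives a value through the top-up rule or is left missing. Leave the paper and electronic diary rule as it is.

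The cost is one phrase in each of two sections, a small programming change, and at most one diary day for each woman who terminates early. Excluding the day removes this bias term entirely. If the sponsor always meant the rule to cover both, the edit only records that, and it should be made before database lock.

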2.2.2 Exploratory Endpoints

- Frequency of VMS, which is the average daily frequency of moderate to severe VMS, defined as the sum of the number of moderate to severe VMS during 1 week divided by number of days with data.
- Severity of VMS, which is the average daily severity score of mild to severe VMS. Baseline VMS severity score is defined as $(2xFmo + 3xFse)/(Fmo + Fse)$, and VMS severity score for a specific week during the open label treatment period is defined as $(1xFmi + 2xFmo + 3xFse)/(Fmi + Fmo + Fse)$, where Fmi, Fmo, and Fse are the daily frequencies of mild, moderate, and severe VMS, respectively, during each applicable study week.
- MENQOL.

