## **3. STUDY DESIGN**

### **3.1 Study Design**

[figure not shown]
Study MT-8554-A02 is an open-label, long-term safety extension trial of Study MT-8554-A01. The study will be initiated during the conduct of Study MT-8554-A01.

Subjects who complete the preceding trial (Study MT-8554-A01) and comply with eligibility criteria for Study MT-8554-A02 will be enrolled in a 52-week open-label treatment period. Visit 7 (Week 12) of Study MT-8554-A01 will be considered Visit 1 of Study MT-8554-A02. Assessments already carried out at Visit 7 (Week 12) of Study MT-8554-A01 will not be repeated. During the 52-week open-label treatment period, subjects will attend visits every 8 weeks between Visits 1 and 3 (Weeks 12, 20, and 28) and every 12 weeks between Visits 3 and 6 (Weeks 28, 40, 52, and 64).

All enrolled subjects will receive MT-8554 (10 mg initially, switched to 5 mg\*) for 52 weeks. Study drug will be administered once daily before bedtime.

An End of Study (EOS) Follow-up visit will be conducted by phone for safety follow-up 30 days after the end of the open-label treatment period.

\*Note: Based upon the results of Study MT-8554-A01, the dose is changed from 10 mg to 5 mg because participating subjects will no longer derive potential clinical benefit from receiving 10 mg dose. All participating subjects who reconsent to continue the study will receive MT-8554 5 mg.

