**Table 1 Schedule of Assessments**

Study Period	Open-label extension						Follow-up
	Visit 1 	Visit 2	Visit 3	Visit 4	Visit 5	Visit 6 (EOT)	
Visit Number							Visit 7 (EOS)
Study Week 	Week 12 	Week 20	Week 28	Week 40	Week 52	Week 64 	Week 68 
Study Day ±Window 	Day 85 ±3	Day 141 ±7	Day 197 ±7	Day 281 ±7	Day 365 ±7	Day 448 ±7	Day 476 ±7
Informed consent	X						
Inclusion/exclusion criteria	X						
Physical examination 	X	X	X	X	X	X	
Breast examination	X						X
Body weight	X			X			X
Vital signs 	X	X	X	X	X	X	
12-lead ECG	X			X			X
Routine lab tests	X	X	X	X	X	X	
Transvaginal ultrasound 	X						X
Endometrial biopsy 	X						X
Reproductive hormones 	X						X
PHQ-8 and GAD7	X		X				X
VMS diary	<—————>						
MENQOL	X		X				X
Dispensing MT-8554 	X	X	X	X	X		
Drug accountability	X	X	X	X	X	X	
Adverse events	<—————>						
Concomitant medication	<—————>						
Compliance █ Calls to Subjects 	<—————>						

Abbreviations: ECG=Electrocardiogram; EOS=End of Study; EOT=End of Treatment Visit; GAD7=Generalized Anxiety Disorder-7 Questionnaire; MENQOL=Menopause Specific Quality of Life; PHQ-8=Eight-Item Patient Health Questionnaire; VMS=vasomotor symptoms.

1. Visit 7 (Week 12) of Study MT-8554-A01 will be considered Visit 1 of Study MT-8554-A02.
2. Study weeks and study days are in reference to the randomization performed on Day 1 in Study MT-8554-A01.
3. Assessments already carried out at Week 12 of Study MT-8554-A01 will not be repeated.
4. The EOT should be performed for subjects who complete treatment as well as those who withdraw from the study early.
5. The Follow-up visit, EOS, will be conducted by phone 30 days after the EOT visit for subjects who complete as well as those who withdraw early from the study.
6. Physical examination (abdominal, cardiovascular, general appearance, respiratory, and other) will be performed.
7. Vital signs (including sitting blood pressure, pulse rate, and tympanic body temperature) will be measured at all visits.
8. Transvaginal ultrasound and endometrial biopsy to be performed only on subjects who have a uterus. Pelvic examination will be performed only with endometrial biopsy.
9. Luteinizing hormone (LH), follicle stimulating hormone (FSH) and estradiol (E2) will be measured.

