## **7. DATA CONVENTION**

### **7.1 Data Handling Convention for Dropouts or Missing Data**

For each summaries, only observed data will be used. Unless otherwise specified missing data will not be imputed. Unless otherwise specified, summary statistics will be calculated as long as one non-missing value exists.

For AE start and/or end date missing or partial missing, the AE will be treated as TEAE if it cannot be determined a non-TEAE. If severity or relationship is found to be missing the most severe occurrence will be imputed for the particular summary.

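### The VMS diary baseline is not tied to the first A02 dose and can include up to 3 post-dose days of 7, and the diary top-up rule needs limits

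*SAP*

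**What the plan says.** SAP 7.3.3.1 averages the daily count of moderate to severe VMS over 7-day windows set out in SAP Table 5. SAP 7.3.3.2 uses the same windows for severity. On the anchor it says: "The nominal day for each time point relative to the first dose day will be used". It does not name the study. The footnote to SAP Table 1 reads: "Study weeks and study days are in reference to the randomization performed on Day 1 in Study MT-8554-A01".

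- **Windows (SAP Table 5).** Baseline (Week 12) is Days 79 to 85. Week k runs from Day 7k−5 to Day 7k+1, for k = 13 to 64.
- **Visits (SAP Table 1).** Visit 1 is Day 85 ±3 and the end-of-treatment (EOT) visit is Day 448 ±7.
- **Dosing (SAP 3.1).** "Study drug will be administered once daily before bedtime".
- **Sparse weeks.** With fewer than four diaries in a week, "the latest diaries in the previous window can be carried as needed to make 4 diaries available in this window". Section 7.3.3.2 repeats this for severity.
- **Last visit.** "VMS data on the day of Week 64 visit is not used for the calculation of average daily VMS frequency". Protocol 5.2.1.3 lists "VMS diary collection" at Visit 6, so no diary days follow it.

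On baseline in general, protocol 10.3.1 takes the last valid value before the first A02 dose. SAP 7.2 has the same default but allows exceptions, and then says that diary endpoints have their own windows. SAP Section 10 says that the severity baseline comes from the end of A01 treatment.

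On missing data, protocol 2.2.2 gives VMS frequency as "defined as the sum of the number of moderate to severe VMS during 1 week divided by number of days with data". SAP 7.1 says "For each summaries, only observed data will be used", subject to exceptions stated elsewhere in the SAP.

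**The concern.** A change from baseline in an extension study should start from data recorded before the extension drug. Table 5 ties baseline to the calendar of the preceding study, and nothing in SAP 7.3.3 ends the window at the first A02 dose. A woman whose Visit 1 comes early but within its window can therefore have A02-treated days counted as baseline, and every later change value for her is measured from that mixture.

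The top-up rule raises a second question, about what a weekly value represents. It has no lower limit on a woman's own diaries, and it does not exclude baseline as the previous window. A reported week can thus contain few or none of its own days, and the table would not show it.

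VMS frequency and severity are the only measures of the secondary objective on long-term VMS efficacy (SAP 2.1 and 8.3), so the rule should be unambiguous even though the analysis is descriptive.

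**Working it through.** **1. Reproduce Table 5.** For k = 12, 7×12−5 = 79 and 7×12+1 = 85, as printed. If the first dose day meant the first A02 dose, Day 85 would lie 12 weeks into A02 treatment and could not be baseline. The anchor must be A01. For k = 63 the window is Days 436 to 442. For k = 64 it is Days 443 to 449, with nominal Day 449; SAP Tables 1 and 3 give Day 448 for the same visit, a one-day mismatch.

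**2. Baseline.** Assume that the first A02 dose is taken at bedtime on the Visit 1 day, so that day's diary is mostly pre-dose. Post-dose days in baseline are the days in 79 to 85 that fall after Visit 1.

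| Visit 1 on Day | Post-dose baseline days | Share of 7 |
|---|---|---|
| 82 | 83, 84, 85 | 3/7 = 43% |
| 83 | 84, 85 | 2/7 = 29% |
| 84 | 85 | 1/7 = 14% |
| 85 to 88 | none | 0 |

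Three of the seven permitted visit days are affected. Let P be the mean daily count before the first A02 dose, T the mean just after it, and m the number of post-dose days, with all diaries complete. The computed baseline is P + (m/7)(T − P), so each later change is off by (m/7)(P − T). If the drug lowers the count at once, the later reduction is understated by up to 43% of that early drop.

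**3. Top-up into Week 13.** The window before Week 13 is baseline. A woman with j diaries in Week 13, j below 4, receives 4 − j baseline diaries. With j = 2, half of her Week 13 value is baseline.

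**4. Top-up after stopping.** A woman whose diary ends in week k has no diaries in week k+1. The rule can supply four from week k and so give her a value for a week in which she recorded nothing.

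**5. Top-up at Week 64.** Own diaries are the days in 443 to 449 before the EOT visit. EOT is permitted on Days 441 to 455. With complete diaries:

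| EOT on Day | Own diaries | Carried from Week 63 | Days used |
|---|---|---|---|
| 441 | 0 | 4 | 437–440 |
| 442 | 0 | 4 | 438–441 |
| 443 | 0 | 4 | 439–442 |
| 444 | 1 | 3 | 440–443 |
| 445 | 2 | 2 | 441–444 |
| 446 | 3 | 1 | 442–445 |
| 447 / 448 / 449 | 4 / 5 / 6 | 0 | own days only |
| 450 to 455 | 7 | 0 | own days only |

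A top-up applies on 6 of 15 permitted days, and on 3 of 15 the value is entirely carried. The documents give no distribution of visit days. For illustration only, EOT days spread evenly would give 40% of women with a top-up. A normal spread around Day 448 with an SD of 2, 3 or 4 days would give 23%, 31% or 34%, and an all-carried value in 1%, 6% or 11%.

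**The case against.** The best defence on baseline is that the documents already intend a pre-dose value. Protocol 10.3.1 says so, SAP Section 10 takes severity from the end of A01, and protocol 6.7.1 starts the A02 diary at Visit 1. This makes the problem a conflict between rules. It does not remove it, because SAP 7.2 passes diary endpoints to Table 5, which has no cut-off at first dose. It is also fair that the effect is uneven: a woman from the A01 10 mg arm who began A02 on 10 mg stayed on the same assigned dose, so her T and P may differ little.

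On Week 64, the topped-up value is simply the last four diary days before EOT. A 7-day window ending before EOT would use those days and three older ones. That stands: the defect there is mainly one of labelling. Numbering from A01 also looks deliberate, since protocol 10.3.1 foresees combining A01 and A02 data, so there is no need to re-anchor every weekly window.

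A reader might infer more than the documents support:

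- **That Week 64 is often carried data.** No visit-day or diary-completion figures are given, and EOT on Day 448 with complete diaries needs no top-up.
- **That carrying repeats week after week to Week 64.** The SAP allows carrying only from the previous window. It does not say that carried diaries count as available for the next one.
- **That 10 mg diaries distort a 5 mg comparison.** The dose-change tables in SAP 8.4 cover exposure, adverse events and ultrasound, with no VMS table.
- **That the top-up is an undeclared protocol departure.** Protocol 10.3.2 leaves missing-data handling to the SAP, and SAP 7.1 allows stated exceptions.

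**Conclusion.** The point holds in a limited form. If Table 5 governs and dosing starts on the evening of Visit 1, a visit on Days 82 to 84 puts 3 to 1 of 7 post-dose days into baseline, contrary to protocol 10.3.1 and out of line with SAP Section 10. The changes from baseline of those women are then measured from a partly treated baseline. How many women this affects cannot be read from the documents.

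The top-up rule can also mix baseline into Week 13, create a value for a week without diaries, and fill Week 64 partly or wholly with Week 63 diaries for an EOT visit on Days 441 to 446. These are possibilities under the rule, with unknown frequency.

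The impact is modest. VMS frequency and severity are labelled exploratory and summarised descriptively, no sample size rests on them, and the primary objective is safety. The correction is still worthwhile because two written baseline rules disagree.

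**What to change.** 1. For frequency and severity, define baseline as the last 7 diary days up to and including the day of the first A02 dose. The dosing day is kept because dosing is at bedtime. No Visit 1 day from 82 to 88 then puts a later post-dose day into baseline.
2. In SAP 7.3.3.1, state which study's first dose sets the day count, and reconcile Day 449 with Day 448.
3. Do not carry baseline diaries into Week 13, and do not carry into any week with no diaries of its own. Set such weeks to missing.
4. Take the end-of-treatment value from the 7 diary days before the EOT visit and label it EOT. With complete diaries, all 15 permitted EOT days then supply 7 diaries.
5. The other weekly windows can stay on A01 numbering. One consequence needs a sentence: with Visit 1 on Day 86, 87 or 88, the new baseline overlaps Week 13 by 1, 2 or 3 days. If those days are left out of Week 13, 6, 5 or 4 remain, still at least four with complete diaries.

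The cost is SAP wording, some programming and a few more missing subject-weeks. The EOT value will overlap the last weekly windows, so it should be shown beside the weekly series and not as a further week in it.
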